##### Radiological endpoints

###### Primary

- The VTT position in relation to the IVC for the Mayo classification will be performed using a combination of both MRI and CT.

###### Secondary

- RECIST 1.1 criteria will be used for CT evaluation

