## 5.2. Schedule of Assessments

### 5.2.1. Screening Procedures

Screening procedures within 4 weeks prior to study enrolment.

- Clinical assessment
  - Signed informed consent
  - Medical history
  - ECOG & Karnofsky performance status (appendix 1)
  - Body weight
  - Height
  - Blood pressure
  - Heart rate
  - Respiratory rate
  - Temperature
  - Symptom assessment (CTCAE V4)
- Histological assessment
  - Confirmation of diagnosis of ccRCC via image guided biopsy (5 cores should be taken for diagnosis/research as per the 'translational research studies' in appendix 6)
- Laboratory determinations
  - FBC, coagulation, glucose, renal and liver function, serum calcium, C - reactive protein (CRP) and Lactate Dehydrogenase (LDH).
  - Urinalysis
  - Serum thyroid function tests (Free T4 and Thyroid stimulating hormone (TSH)).
  - Pregnancy Test (serum or urine) if applicable (must be performed a maximum of 14 days prior to receiving 1st dose of axitinib)
- Radiological assessment
  - CT thorax, abdomen and pelvis for IVC VTT and primary tumour assessment using RECIST 1.1 criteria and the Mayo classification
  - Diffusion/ contrast enhanced MRI abdomen

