#### **5.2.4. Assessment at day 1, week 3 (within 7 days)**

- Laboratory determinations
  - FBC, coagulation, glucose, renal and liver function, serum calcium, CRP and LDH
  - Urinalysis
  - Serum thyroid function tests (Free T4 and TSH)
  - Blood and urine sample for biomarker analysis (NB. patients should be asked to fast for 6 hours prior to urine analysis)
- Clinical assessment
  - ECOG & Karnofsky performance status (appendix 1)
  - Body weight
  - Height
  - Blood pressure
  - Heart rate
  - Respiratory rate
  - Temperature
  - Symptom assessment (CTCAE V4)
  - Assessment for concomitant medications
  - Assessment of compliance with study medication
  - Dose evaluation and escalation (where appropriate)
- Radiological assessment
  - CT chest for IVC VTT (M0 patients only) to check for development of metastasis
  - Diffusion/ contrast enhanced MRI abdomen (all patients)
- Pharmacy
  - Dispense axitinib (dose modification as per section 4.2 if applicable)

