**5.2.7. Assessment at day 1, week 9 (within 7 days)**

- Laboratory determinations
  - FBC, coagulation, glucose, renal and liver function, serum calcium, CRP and LDH
  - Urinalysis
  - Blood and urine sample for biomarker analysis (NB. patients should be asked to fast for 6 hours prior to urine analysis)
- Clinical assessment
  - ECOG & Karnofsky performance status
  - Body weight
  - Height
  - Blood pressure
  - Heart rate
  - Respiratory rate
  - Temperature
  - Symptom assessment (CTCAE V4)
  - Assessment of compliance with study medication
- Radiological assessment
  - CT thorax, abdomen and pelvis (M1 patients) for IVC VTT and primary tumour assessment using RECIST 1.1 criteria and the Mayo classification
  - CT chest (M0 patients) for IVC VTT to check for development of chest metastasis.
  - Diffusion/ contrast enhanced MRI abdomen (all patients)

The patient should stop axitinib a minimum of 36 hours and a maximum 7 days prior to surgery; no further study drug should be dispensed.

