#### **5.2.11. Imaging**

- All imaging data will be collated centrally.
- CT and RECIST assessment will be undertaken locally.
- MRI assessment will be undertaken at a single site to ensure consistency.

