- The percentage of patients who have had a change in the surgical approach will be calculated with the percentage with a less invasive and the percentage with a more invasive approach shown separately. Two pieces of data are relevant here: (1) a change from “Open Surgery” to “Minimally invasive surgery”; and (2) a change from a more invasive open to a less invasive open surgical approach (see [Section 6.1](#) for a definition of surgical approach in this respect). Percentages will be calculated using both the evaluable population and the ITT population.
- The response rate, as determined by RECIST criteria v1.1 and provided by sites will be presented and the percentage of outcomes categorised as complete response, partial response and progressive disease shown; only pre-surgical timepoints (i.e., weeks 3 and 9) will be considered. To provide further quality assurance that these RECIST evaluations are correct, the RECIST response will be recalculated from source data by the study statistician and compared to the evaluations provided by sites. Should the evaluations not correspond with each other, a data query will be raised with the sites.
- Morbidity, in terms of the Clavien-Dindo classification system will be presented and percentage of patients with complications of grade I to V will be presented. Percentages will be calculated using both the evaluable population and the ITT population.

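### RECIST response is to be reported for all patients at weeks 3 and 9, but the CT it is attached to is scheduled on treatment only for M1 patients at week 9

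*Protocol*

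**What the plan says.** RECIST response is a secondary endpoint. The screening visit (Protocol 5.2.1) attaches it to a full CT: "CT thorax, abdomen and pelvis for IVC VTT and primary tumour assessment using RECIST 1.1 criteria and the Mayo classification". Protocol 5.2.11 says under its secondary radiological endpoint that "RECIST 1.1 criteria will be used for CT evaluation". It also separates the readers: "CT and RECIST assessment will be undertaken locally", whereas "MRI assessment will be undertaken at a single site to ensure consistency".

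SAP Section 6 takes the endpoint from the sites: "The response rate, as determined by RECIST criteria v1.1 and provided by sites will be presented". On timing, "only pre-surgical timepoints (i.e., weeks 3 and 9) will be considered". The study statistician recalculates the category from source data and queries disagreements. SAP 7.6.2 then uses the site's pre-surgical RECIST category to stratify change in thrombus length and to colour the waterfall plot, without saying which visit supplies it.

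The visit schedules order less CT than this needs. At week 3 (Protocol 5.2.4) the only CT is "CT chest for IVC VTT (M0 patients only) to check for development of metastasis". At week 9 (Protocol 5.2.7) M1 patients have the full CT, but M0 patients have "CT chest (M0 patients) for IVC VTT to check for development of chest metastasis". Contrast-enhanced abdominal MRI is scheduled for everyone at screening, week 3 and week 9. The schedule table in Protocol 5.1 agrees with the visit text.

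**The concern.** The plan asks for a response category at two visits in two groups of patients and names CT as the method. For three of those four combinations the named scan is not ordered. No section says which modality measures abdominal lesions for RECIST response when there is no abdominal CT.

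If sites follow the CT wording, M0 patients have no measurement of the primary after screening. If sites fill the gap themselves, some will set a screening CT diameter against a later MRI diameter, and the difference between methods enters the change that defines the category. The statistician's recalculation would then raise queries that reflect modality, not error. The thrombus-length stratification and the waterfall plot inherit the problem. An M1 patient recorded as stable at week 3 could have chest progression that no scan was ordered to show.

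**Working it through.** No stated figure in the plan bears on this point, so there is none to reproduce. The check sets the imaging schedule against the reporting rule.

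Scheduled imaging (Protocol 5.1, 5.2.1, 5.2.4, 5.2.7):

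| Visit | M0 | M1 |
|---|---|---|
| Screening | CT chest/abdomen/pelvis; MRI abdomen | CT chest/abdomen/pelvis; MRI abdomen |
| Week 3 | CT chest; MRI abdomen | MRI abdomen |
| Week 9 | CT chest; MRI abdomen | CT chest/abdomen/pelvis; MRI abdomen |

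Each of the four on-treatment cells (two stages by two visits) was tested under two rules.

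| Cell | Rule A: chest and abdomen both on CT | Rule B: chest on CT, abdomen on CT or MRI |
|---|---|---|
| M0 week 3 | no | yes |
| M0 week 9 | no | yes |
| M1 week 3 | no | no (chest not imaged) |
| M1 week 9 | yes | yes |
| Total | 1 of 4 | 3 of 4 |

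No other scheduled CT fills the gap. The next abdominal CT for an M0 patient is at 12 weeks after surgery (Protocol 5.2.10), when the primary has been removed, and the SAP restricts response to pre-surgical visits. Protocol 4.2 gives a post-treatment CT to patients permanently stopped for toxicity, which is an off-schedule exception.

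Number of patients, with a target of 20:

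- Week 3: no M0 or M1 patient has a scheduled abdominal CT, so 20 of 20 lack a CT measurement of the primary.
- Week 9: the M0 share is not given. At an assumed 30%, 0.30 × 20 = 6 patients lack one. At an assumed 70%, 0.70 × 20 = 14 do.
- SAP 8.1 considers multiple imputation when a secondary outcome is more than 10% missing, that is, more than 0.10 × 20 = 2 patients. Under Rule A, week 9 response would be missing for 30% to 70% across the assumed range. The data would be absent by schedule for every M0 patient, so only M1 patients would supply observed responses to impute from.

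Under Rule B the M0 cells can have a like-for-like baseline, because the same MRI is acquired at screening. That holds only if the screening diameter is also taken from MRI, and nothing in the plan requires this.

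**The case against.** The strongest reply is that CT-only RECIST is an inference. The sentence in Protocol 5.2.11 says how CT is evaluated; it does not exclude MRI. Protocol 3.4 sends week 3 abdominal MRI to central review for RECIST progression, and SAP Section 2 does the same with MRI and CT from weeks 0, 3 and 9. Every patient has abdominal MRI at all three times. The SAP also mentions an MRI SOP that is not among the documents and might cover lesion diameters. The in-house recalculation is only to be compared where possible.

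Much of this stands. A reader might infer that the RECIST endpoint cannot be derived at all; the documents do not support that. M1 week 9 response has paired full CT and works under any reading, and the imaging needed for M0 response exists. A reader might also infer that the response rate is open to manipulation by dropping M0 patients from the denominator. That is not supported either: SAP 4.3 and 6.1 set the denominators as the evaluable or ITT population, and evaluable means at least one dose.

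The reply does not close the gap. The MRI provisions concern progression, and the RECIST review applies only where a site is in doubt; they do not define how response is measured. RECIST stays a local, site-provided assessment while MRI is read at another place, and no link between the two is described. Accepting MRI also leaves the M1 chest unseen at week 3.

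**Conclusion.** The reporting rule and the imaging schedule do not match, and the plan should be amended. M1 week 9 response is derivable as written. M0 response at weeks 3 and 9 is derivable only if abdominal MRI is accepted for response; without a rule on this, a CT baseline may be compared with an MRI follow-up. A full week 3 response for M1 patients with chest lesions is not derivable under either reading.

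The coverage counts (1 of 4, or 3 of 4) follow directly from the schedule. The figure of 6 to 14 patients rests on an assumed M0 share of 30% to 70%. The contents of the MRI SOP are unknown and could settle part of the measurement question.

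The stakes are moderate. RECIST is one of four secondary endpoints, reported descriptively in a 20-patient feasibility study. The primary Mayo endpoint is assessed on MRI and CT together and is unaffected.

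**What to change.** Amend Protocol 5.2.11 and SAP Sections 6 and 7.6.2 as follows.

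1. Measure each target lesion by the same method at baseline and follow-up. For M0 patients, use the abdominal MRI at screening and week 9 for abdominal lesions, and CT for the chest. For M1 patients, keep the paired chest, abdomen and pelvis CT at screening and week 9, so that pelvic lesions stay covered.
2. Report the RECIST response category at week 9 only, shown separately for M0 and M1 because the modality differs. Name this week 9 category as the one used for the thrombus-length stratification and the waterfall plot.
3. Limit week 3 to a progression flag for the regions imaged, with the M1 chest recorded as not assessed.
4. State how diameters from the single-site MRI read reach the local RECIST assessor and the statistician's recalculation, and who assigns the final category.

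The cost is protocol and SAP wording, plus recording diameters from MRI that is already acquired. No new scans are needed. Two things are given up: week 3 response categories, and a common modality across M0 and M1. The first could be fully supported for M0 patients only, and only if MRI is accepted. The second is why the results should be shown by stage.

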###### Exploratory

- The following exploratory endpoints may also be evaluated on MRI
  - VTT volume will be calculated using the thin slice MRI images reconstructed where appropriate. A small group of readers will undertake this and where possible automated segmentation will be used for consistency.
  - Change in the maximum VTT length using coronal MRI reconstructions
  - Apparent Diffusion Coefficient (DWI) changes over time of both the whole tumour and VTT.
  - Textural features of the whole tumour and VTT on MRI as a measure of heterogeneity, as well as changes in heterogeneity during treatment. This will be measured using semi-automated proprietary software where possible.

### **5.3. Withdrawal of Subjects**

Patients *discontinue* from the study for reasons such as safety, non-compliance or withdrawal of consent, etc. These patients will continue to be followed up for efficacy and safety as per protocol, unless they are lost to follow up, deceased or withdrew consent to the study. The bio-samples collected during the study will continue to be used for translational research.

Patients may *withdraw* from the study at any point; no further data collection will take place, and will be censored at the point of withdrawal this should be indicated on the case report form (CRF) as per completion guidelines.

Patients who consent to the trial but do not start trial treatment will be withdrawn from the trial. These patients will not be followed up as part of the study and will be expedited to surgery as per standard practice.

For any patient that did not start study treatment, a further patient would be enrolled to the trial to maintain the target number of patients for analysis.

## **6. Translational Research**

Tissue, blood and urine will be collected at baseline (all sample types), throughout the 8 week treatment period (blood and urine) and at surgery (all sample types). A minimum requirement will be access to a formalin-fixed, paraffin-embedded tumour block (excess to diagnostic requirements) from the patient biopsy and nephrectomy. Where the institutional infrastructure exists the following samples will be collected: fresh frozen tissue (biopsy and nephrectomy), fresh tissue (biopsy and nephrectomy) plasma, buffy coat, urine, and peripheral blood mononuclear cells (PBMCs). The analysis streams will be as follows, with the aim of identifying molecular correlates to the clinical outcomes of this study.

### **6.1. Circulating tumour DNA (ctDNA)**

In view intratumoural heterogeneity, the use of tumour tissue for the development of prognostic and predictive biomarkers in ccRCC is challenging (20). Circulating tumour DNA (ctDNA) has been established to represent the tumour biology and may be superior to tissue as heterogeneity will be negated (21). Obtaining ctDNA from blood from patients with VTT is the ideal platform on which to validate ctDNA in RCC because of the high likelihood of DNA shedding from the tumour directly into the circulation. Furthermore, the change in ctDNA profiles from baseline to treatment phase to post-treatment phase may be informative regarding markers of tumour response.

### **6.2. Metabolomics**

It is well established that there is a strong metabolic basis to ccRCC. The presence of the Warburg effect has revealed several novel targets for treatment or tumour surveillance (22). Metabolites will be assayed in urine, blood and tissue across the various time points of the NAXIVA study to assess the use of these molecules in patients with VTT and with axitinib therapy.

### **6.3. Predictive biomarker studies**

There has been previous identification of a prognostic biomarker signature for response to sunitinib. The same biomarker profile will be validated for axitinib using the matched biopsy and nephrectomy tumour tissue samples obtained in this study.

#### **6.4. Comparative study of IVC VTT in untreated and treated patients**

Dovetailing in with ongoing studies looking at the invasive front of the IVC VTT in TKI naïve patients, the VTT samples from NAXIVA will be assessed using the same biomarker pipeline specifically searching for evidence in alterations in EMT or invasion profiles. The hypothesis being that treatment with axitinib abrogates some of the invasive features of the VTT.

#### **6.5. Imaging**

There is little published data on the best imaging method for assessing the IVC VTT. USS, CT and MRI are all currently used in different centres. Surgical outcome studies have shown that patients with solid VTT will have a superior oncological outcome compared to friable VTT, yet there are no radiological data on how to make this assessment. A non-invasive imaging biomarker of VTT composition would help to guide surgery in patients with borderline fitness. Textural analysis of the serial CT and MRI scans undertaken as part of NAXIVA will be performed and compared to the surgical outcome to assess if VTT composition and the effect of drug on VTT can be determined on imaging. Renal vein and IVC VTT volumes will be measured using MR venography techniques developed in Cambridge and % changes in post-contrast enhancement within the thrombus will be assessed from dynamic contrast-enhanced MRI (DCE-MRI) data. Exploratory analyses will include: changes in total tumour volume in the renal vein and IVC (CT and MRI); changes in the degree of enhancement after intravenous contrast administration (MRI); changes in imaging heterogeneity (texture) of the renal and IVC VTT (CT and MRI); differentiation of solid from friable IVC VTT using MR venography and physiological manoeuvres (Valsalva).

#### **6.6. Immune Analysis**

It is known that RCC is a typical immunogenic tumour with immune mechanisms known to play an important role in its natural history. Recent studies have also shown that TKI treatment can influence the immune system and, importantly, changes in the immune response may affect response and survival. The immune aim to identify immune- and cytokine-based signatures in PBMCs, plasma and urine which predict response to axitinib treatment in RCC patients. These studies will also provide important information about the effect of axitinib on the immune system in RCC, and vice versa, including providing comprehensive analysis of how peripheral immune cell populations and cytokines vary during treatment with axitinib, and whether they correlate with other markers of response and resistance in RCC patients. Importantly, it will also provide essential immunological information to inform biologically driven, rational, scheduling of future studies examining combinations of axitinib and immunotherapy.

### **7. PHARMACOVIGILANCE**

#### **7.1. Definitions**

**Adverse Event (AE):** An adverse event (AE) is any untoward medical occurrence in a patient which does not necessarily have a causal relationship with the study treatments or procedures. An adverse event can therefore be any unfavourable and unintended sign (including an abnormal laboratory finding), symptom, or disease temporally associated with a treatment or procedure, whether or not considered related.

**Adverse Reaction (AR):** All noxious and unintended responses related to a study treatment or procedure should be considered adverse drug reactions.

**Serious Adverse Event (SAE):** Any untoward medical occurrence in a patient that

- a) Results in death
- b) Is life-threatening
- c) Requires hospitalisation or prolongation of existing hospitalisation
- d) Results in persistent or significant disability or incapacity
- e) Consists of a congenital anomaly or birth defect
- f) Is otherwise considered to be medically significant by the investigator

The term “life-threatening” refers to an event in which the patient was at risk of death at the time of the event; it does not refer to an event which hypothetically might have caused death if it were more severe.

Hospitalisations planned prior to enrolment in the trial or for social reasons should not normally be considered as SAEs unless the hospitalisation has to be prolonged. Treatment in an emergency room of less than 24 hours or on an out-patient basis that does not meet any other serious criteria should not be considered as an SAE.

Hospitalisation for nephrectomy is not considered a SAE where this goes ahead as planned within the trial. Prolonged hospitalisation, however, should be reported as SAE.

**Suspected Unexpected Serious Adverse Reaction (SUSAR):** A suspected unexpected serious adverse reaction (SUSAR) is an adverse reaction that is classified as serious and it is suspected that it is caused by a study treatment or procedure. The nature, severity or outcome of this adverse reaction also must not be consistent with the current version of the SmPC for the treatment or procedure.

## 7.2. Recording of Adverse Events

All related Adverse Reactions will be recorded in the Case Report Form. Any Adverse Reaction considered unrelated will not be recorded.

All adverse reactions that occur after the signing of written informed consent and within 30 days after the final study treatment will be recorded on the appropriate CRF page. The exception to this would be any event occurring after signing the informed consent and prior to commencing study treatment that is considered unrelated to trial procedures. In addition any events occurring more than 30 days after final study treatment that are deemed to be related to the study drug should be notified to SCTRUM as detailed in section 7.4.

Any medical conditions or diseases present prior to signing of informed consent should only be considered an adverse event if there is a worsening of the condition.

Please refer to Appendix 2 for details on the Causality.

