### Description of causality of adverse events

Possibly Related: No	Unrelated	There is no evidence of any causal relationship.
	Unlikely	There is little evidence to suggest there is a causal relationship (e.g. the event did not occur within a reasonable time after administration of the trial medication). There is another reasonable explanation for the event (e.g. the patient's clinical condition, other concomitant treatment).
Possibly Related: Yes	Possible	There is some evidence to suggest a causal relationship (e.g. because the event occurs within a reasonable time after administration of the trial medication). However, the influence of other factors may have contributed to the event (e.g. the patient's clinical condition, other concomitant treatments).
	Probable	There is evidence to suggest a causal relationship and the influence of other factors is unlikely.
	Definitely	There is clear evidence to suggest a causal relationship and other possible contributing factors can be ruled out.

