5.1 Adverse events, SAEs and SUSARs

All reported adverse events (including adverse reactions, SAEs and SUSARs) will be presented, with events categorised against the National Cancer Institute Common Terminology Criteria for Adverse Events v4.0.

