7.5.4 Toxicities (including adverse events and laboratory values) (Safety population)

- All adverse events will be coded according to the CTC toxicity criteria and the worst value over the study drug periods determined for each patient.
- Laboratory values will be coded according to the CTC toxicity criteria and the worst value over the study period determined for each patient.
- Any adverse events or laboratory anomalies which are graded \geq grade 1 by at least 10% of patients will be tabulated.
- Details of toxicities will be summarised to show (i) grade at trial entry; (ii) the highest grade over the course of treatment; and (iii) the highest grade in follow up. For any toxicity graded \geq grade 2 at any timepoint, the toxicity grading will be tracked over the course of the trial in a graphical form.

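### The protocol puts only drug-related adverse reactions on the CRF, the planned analyses summarise all adverse events, and the SAP does not say which data source feeds its toxicity tables.

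*Protocol*

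**What the plan says.** **Recording.** Protocol 7.2 states: "All related Adverse Reactions will be recorded in the Case Report Form". It then adds: "Any Adverse Reaction considered unrelated will not be recorded". The window runs from consent and covers reactions "within 30 days after the final study treatment will be recorded on the appropriate CRF page". Events before the first dose that are unrelated to trial procedures are exempt. Protocol 7.1 has already defined the term: "All noxious and unintended responses related to a study treatment or procedure should be considered adverse drug reactions". The causality table in Appendix 2 has two categories under Possibly Related: No. One is unrelated. The other is unlikely, described as "There is little evidence to suggest there is a causal relationship".

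**Analysis.** The Final Analysis part of protocol 9.2 summarises the worst CTCAE grade of adverse events, with no limit to related ones. Protocol 8.1 lists adverse events among the data collected. SAP 5.1 states: "All reported adverse events (including adverse reactions, SAEs and SUSARs) will be presented". SAP 7.5.4 states: "All adverse events will be coded according to the CTC toxicity criteria". It asks for a summary showing "i) grade at trial entry; (ii) the highest grade over the course of treatment", and then the highest grade in follow-up. It also tabulates events of grade 1 or above that occur in at least 10% of patients.

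**Other safety data.** Protocol 5.1 schedules CTCAE v4 symptom assessment at screening, at day 1, at weeks 3, 5, 7 and 9, and 6 and 12 weeks after surgery, with no causality condition. SAP 7.3 lists existing signs and symptoms with their grades at baseline. SAP 7.5.4 codes laboratory values directly. Protocol 7.3 records serious events whatever their cause once treatment has started.

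**The concern.** The recording rule and the planned tables do not describe the same data. The SAP treats adverse reactions as a subset of what it will present, whereas protocol 7.2 makes them the whole of what is recorded as events outside the serious-event form. The rule is also hard to apply as written: under the definition in 7.1 a reaction is related, so an unrelated reaction cannot exist.

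This matters because the trial has one open-label arm. No control group can show that events put down to the cancer or to comorbidity are more frequent than expected. An event left off the CRF cannot be recovered by any later analysis. Protocol 1.5 names adverse events that could affect fitness for surgery as a risk of the eight-week treatment, and that risk depends on all events, not only those attributed to axitinib. If filtered and unfiltered sources are mixed in one table without labels, a reader cannot tell what the rates mean.

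**Working it through.** The documents give no figure to reproduce here. The check has three parts.

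**1. Which safety data pass through the attribution rule**

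| Data | Where planned | Filtered by attribution? |
|---|---|---|
| Grade at trial entry | Protocol 5.2.1 and 5.2.3; SAP 7.3 | No |
| Symptoms graded at visits | Protocol 5.1, 5.2.3 to 5.2.7, 5.2.9, 5.2.10 | No |
| Laboratory toxicities | SAP 7.5.4 | No |
| Serious events after treatment starts | Protocol 7.3; SAP 7.5.5 | No |
| Non-serious clinical events not captured at a scheduled assessment | Protocol 7.2 | Yes |

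Only the last row is exposed. Whether it includes events judged unlikely to be related is not settled: protocol 7.2 says unrelated, and Appendix 2 keeps the two categories apart but places both on the not-related side.

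**2. Whether the reaction page could supply the follow-up column**

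- Axitinib stops 36 hours (1.5 days) to 7 days before surgery (protocol 3.1).
- The window closes 30 days after the last dose. Counted from surgery, that is 30 − 7 = 23 days to 30 − 1.5 = 28.5 days.
- The first follow-up visit is at 6 weeks, within 7 days: 42 ± 7, or days 35 to 49.

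The window closes before the first follow-up visit. The follow-up column in SAP 7.5.4 therefore cannot come mainly from the reaction page. It fits the visit grades and laboratory values, although the SAP does not say so.

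**3. Size of the effect if a table used the reaction page alone**

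Let p be the true rate of an event, whatever its cause, and a the share of cases judged related and so recorded. Both are assumed, and patients are taken as independent. The recorded rate is q = p × a. The 10% threshold is 0.10 × 20 = 2 patients, and

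P(at least 2 of 20) = 1 − (1 − q)^20 − 20q(1 − q)^19.

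Worked case: p = 0.20 and a = 0.7 give q = 0.14, and the probability is 0.792.

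| True rate p | a = 1.0 | a = 0.7 | a = 0.5 |
|---|---|---|---|
| 0.10 | 0.608 | 0.413 | 0.264 |
| 0.20 | 0.931 | 0.792 | 0.608 |
| 0.50 | 1.000 | 0.998 | 0.976 |

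For p = 0.20 the expected number of recorded cases falls from 20 × 0.20 = 4 to 20 × 0.14 = 2.8, or to 20 × 0.10 = 2. For p = 0.50 the event is almost always displayed, although its recorded rate would still fall in proportion to a.

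The planned table is of all events. Its rate is therefore too low even when every attribution is correct, because correctly excluded unrelated events are missing as well.

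**The case against.** The strongest reply is that the safety plan does not rest on the reaction page. Symptoms are graded by CTCAE at each treatment visit and at both follow-up visits regardless of cause, laboratory toxicity needs no attribution, and serious events are captured whatever their cause. The SAP's request for entry, treatment and follow-up grades, and for grades plotted over time, looks designed for visit data. Fitness for surgery is also covered by performance status at each visit, reasons for stopping drug, reasons surgery was not performed, and Clavien-Dindo morbidity. The 10% threshold limits one tabulation only, since SAP 5.1 presents all reported events.

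Most of this stands, and it rules out a stronger reading that a reader might infer: that every toxicity table will be filtered by attribution, or that the SAP's tables cannot be built because an entry grade can never be drug-related. Entry grades come from the screening and baseline assessments, so that argument fails.

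The reply does not remove the gap. It relies on the tables being built from visit data, which no section states. SAP 5.1 covers only events that were reported, so it cannot restore one that protocol 7.2 kept off the CRF.

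**Conclusion.** The point holds in limited form. Protocol 7.2 conflicts with protocol 9.2 and with SAP 5.1 and 7.5.4. It also conflicts with the definition in protocol 7.1, and the SAP leaves the source of its toxicity tables unstated. The exposed part is non-serious clinical events judged unrelated, possibly also those judged unlikely, that no scheduled symptom assessment captures. Any table drawn from the reaction page would understate these.

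The effect on display is material for less common events and slight for common ones: at a = 0.5 the chance of reaching the threshold falls from 0.931 to 0.608 for a 20% event, but only to 0.976 for a 50% event. These figures rest on assumed event rates and assumed shares judged related, because the documents give neither. They also suppose a table built from the reaction page alone. If the tables use visit grades, and those grades are entered on the CRF, the loss is smaller. The primary efficacy analysis is not affected.

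**What to change.** **Protocol 7.2.** Record all adverse events, whatever their cause, with the Appendix 2 causality grade as a field. Keep the present window, from consent to 30 days after the last dose, with the existing exception for pre-treatment events unrelated to trial procedures. Starting at first dose instead would lose procedure-related events, such as those from the research biopsy. Remove the reference to unrelated reactions. Correct the pointer for late events, which names section 7.4 (the annual safety report) and appears to mean 7.3.

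**SAP 7.5.4.** Tabulate all-cause and treatment-related events side by side. State the data source of each table, and take the follow-up column from the scheduled 6- and 12-week CTCAE and laboratory assessments.

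If the recording rule has to stay, the minimum is to name each source and label any table built from the reaction page as treatment-related only.

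**Cost.** Slightly more CRF entry for about 20 patients whose symptoms are already graded at visits, and a short edit to each document. It is a cheap improvement.
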